## **8.2 Anticipated Adverse Events:**

Mild allergic reaction to sensor material and adhesives.

Redness or skin irritation from sensor material and adhesives.

## **8.3 Adverse Event Reporting:**

- All Adverse Events, both Anticipated and Unanticipated, must be recorded in the CRF and recorded in detail in the Adverse Event Report Form.
- All Adverse Events must be promptly reported to the Sponsor.
- All Unanticipated Adverse Device Effects will be also reported to both the Sponsor and the IRB.
- Both Serious Adverse Events and Unanticipated Adverse Device Effects must be reported to the Sponsor within 48 hours. All other Adverse Events should be reported to the Sponsor within 5 business days.
- All Serious Adverse Events will be also reported to the IRB per IRB reporting requirements. These reports may include, but will not be limited to: date of onset; brief description of the events; their treatment; whether they resulted in death, inpatient hospitalization, severe or permanent disability or were life threatening; their relationship to the study device; and resolution.

## **Deviations from the study protocol**

Deviations from the protocol must receive both Sponsor and the investigator's IRB approval before they are initiated. Any protocol deviations initiated without Sponsor and the investigator's IRB approval that may affect the scientific soundness of the study, or affect the rights, safety, or welfare of study subjects, must be reported to the Sponsor and to the investigator's IRB as soon as a possible, but no later than 5 working days of the protocol deviation.

## **Withdrawal of IRB approval**

An investigator shall report to the sponsor a withdrawal of approval by the investigator's reviewing IRB as soon as a possible, but no later than 5 working days of the IRB notification of withdrawal of approval.

## **9 DATA MANAGEMENT**

### **9.1 Provisions to Protect the Privacy Interests of Subjects**

Potential study candidates will be identified following a review of the elective surgical schedule. The attending surgeon will then be contacted to confirm the appropriateness of the patient and identify any steps that are indicated to protect the subjects' privacy interests. Patient recruitment and informed consent will be obtained when there is sufficient time for a complete discussion between the investigator and the patient. Recruitment will be by direct discussion between the prospective candidates and the study investigators prior to their scheduled surgical procedure. The investigators and/or designated study staff will provide the consent form in person and give the prospective subject sufficient time to review the consent form and discuss the study with friends and family.

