### 2.1 Specific Aims

**Aim One:** to collect raw and processed EEG data with Masimo SedLine monitor while anesthesiologist is blinded to the PSI (Patient State Index) score and to the raw EEG waveforms from the Masimo SedLine monitor in order to establish a Baseline for Standard Practice.

**Aim Two:** to collect raw and processed EEG data with Masimo SedLine monitor while anesthesiologist is monitoring subject using the current (FDA approved) PSI to supplement Standard of Care (SOC) procedures in managing anesthesia.

**Aim Three:** to collect raw and processed EEG data with Masimo SedLine monitor while anesthesiologist is monitoring subjects using the new (investigational) PSI to supplement Standard of Care (SOC) procedures in managing anesthesia.

**Aim Four:** to evaluate the performance of the new (investigational) PSI compared to current (FDA approved) PSI. Comparison measures include frequency of somatic events, total anesthesia drug used, wake up times, PSI versus Observer's Assessment of Alertness/Sedation (OAA/S).

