**4.3 Exclusion Criteria**

- Subjects with any deformities, diseases or for any other reason that may prevent proper fit and application of the SedLine sensors.
- Inability to obtain subjects' physiological, vital, demographics, and real time anesthesia data.
- Subjects who are pregnant.
- Known history of drug abuse.
- Subjects deemed not suitable for study at the discretion of the Principal Investigator.

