## 6 STUDY PROCEDURES

### 6.1 Cohort Enrollment

Each cohort will enroll up to 50 subjects each. Subjects will be assigned to Cohort 1 until up to 50 subjects have been enrolled, after which subjects will be enrolled to Cohort 2. Cohort 2 will enroll up to 50 subjects, after which subjects will be enrolled to Cohort 3, which will enroll up to 50 subjects. All Cohorts will have equal sample sizes.

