### **9.4 Screening and Enrollment Logs**

A subject screening and enrollment log will be provided to study site by sponsor, and maintained by study site. The screening and enrollment log will document, at a minimum, information such as the number of subjects approached for informed consent, the date of consent, subject eligibility, subject enrollment status, subject withdraw (if applicable) and reason(s) for withdrawal.

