### **9.7 Data Analysis**

Data analysis is to be done by Sponsor personnel upon completion of study. Data analysis may include descriptive statistics, regression testing and measures of accuracy (e.g., bias, precision and root mean square of the differences).

Different sets of comparisons could be made between the three Cohorts; data for Cohorts 2 and 3 may be compared against each other, and data for Cohort 2 and Cohort 3 may be compared individually against data for Cohort 1.

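### Staff who choose candidates can know which PSI revision is open, consecutive approach is not required, and the required log starts only at approach, so Cohorts 2 and 3 could be selected differently

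*Combined protocol and SAP*

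**What the plan says.** **Allocation.** Section 6.1 fills the cohorts one after another: "Cohort 2 will enroll up to 50 subjects, after which subjects will be enrolled to Cohort 3". There is no randomisation, and nothing conceals the open cohort from those who recruit.

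**Before approach.** Section 9.1 begins "Potential study candidates will be identified following a review of the elective surgical schedule" and continues "The attending surgeon will then be contacted to confirm the appropriateness of the patient". It does not define appropriateness and does not refer to the criteria in 4.2 and 4.3. Section 4.3 has its own open-ended item: "Subjects deemed not suitable for study at the discretion of the Principal Investigator". No section requires eligible patients to be approached consecutively.

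**Records.** Section 9.4 sets the minimum content of the screening and enrollment log, and its first item is "the number of subjects approached for informed consent". Nothing requires an entry for a candidate who was identified on the schedule but not approached, or a reason for passing that person over. For enrolled subjects, section 4.5 has demographics, comorbidities and medications recorded on the CRF.

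**Use of the data.** Aim Four in section 2.1 is "to evaluate the performance of the new (investigational) PSI compared to current (FDA approved) PSI", with drug totals, wake-up times and somatic events among its measures. Section 9.7 says "data for Cohorts 2 and 3 may be compared against each other". Neither section 7 nor section 9.7 plans a baseline comparison or covariate adjustment between cohorts.

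**The concern.** In a non-randomised comparison with a predictable allocation, the choice of whom to invite is where selection bias can enter. Here that choice passes through two judgements without stated criteria, and people who can know which PSI revision the next patient would get may take part in it.

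Total anesthetic drug and wake-up time plausibly depend on the length and complexity of the case. If complex cases were put forward less often in one of Cohorts 2 and 3, that cohort would tend to show less drug and faster wake-up because of who was invited. The required log could not show this, since its count begins after the selection. This differs from drift over calendar time, which sequential filling also allows: selection could arise with no drift at all, and it can be reduced even if the sponsor keeps sequential cohorts.

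**Working it through.** **1. The plan's own figure.** Section 7 gives power 0.80, α = 0.05, Cohen's d = 0.80, equal groups and a two-sample t-test, and states 26 per group. With a two-sided test the noncentral t solution is n = 25.52, rounded up to 26, so the figure reproduces. At the planned maximum of 50 per cohort, power at d = 0.80 is 97.7%.

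**2. From withheld cases to bias.** The documents give no case-mix figures, so these inputs are assumptions:
- p = 0.25, the share of candidates who are complex cases;
- D = 1 SD, the difference in mean outcome between complex and other cases;
- w, the share of complex cases withheld in one cohort and not in the other.

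The share of complex cases left in the affected cohort is p₂ = p(1 − w)/(1 − pw), and the bias is b = D(p − p₂). For w = 0.50, p₂ = 0.125/0.875 = 0.143 and b = 0.25 − 0.143 = 0.107 SD.

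**3. From bias to false positives.** With no true difference between revisions and n = 50 per cohort, the t statistic has 98 degrees of freedom and noncentrality b√(n/2) = 5b. The two-sided rejection rate at α = 0.05 is then:

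| Withheld (w) | p₂ | Bias (SD) | 5b | False-positive rate |
|---|---|---|---|---|
| 25% | 0.200 | 0.050 | 0.25 | 5.7% |
| 50% | 0.143 | 0.107 | 0.54 | 8.3% |
| 75% | 0.077 | 0.173 | 0.87 | 13.7% |
| 100% | 0 | 0.250 | 1.25 | 23.6% |

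**4. Sensitivity.**
- *Smaller outcome difference.* With D = 0.5 SD the biases halve to 0.025, 0.054, 0.087 and 0.125 SD, and the rates are 5.2%, 5.8%, 7.1% and 9.5%.
- *Meaning of the SD.* If 1 SD is the SD within each type of case, the unselected cohort has variance 1 + 0.25 × 0.75 = 1.1875 and the selected one 1. The pooled SD is √1.09375 = 1.046, the full-withholding bias is 0.25/1.046 = 0.239 SD, and the rate is about 22% instead of 23.6%.
- *Sample size.* More subjects do not help. A 0.25 SD bias gives 14.3% at 26 per cohort and 23.6% at 50. The margin above 26 that section 7 offers as reassurance gives no protection against this.

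**The case against.** **The mechanism is not shown.** A reader might infer that the surgeon steers cases toward or away from the investigational PSI. The documents do not support that. PSI is used by the anesthesiologist; no section tells the surgeon which cohort is open or gives the surgeon a stake in either revision. Section 9.1 concerns privacy, and the contact may be ordinary courtesy to the treating physician. An undefined criterion biases the contrast only if it is applied differently by cohort. This stands as a limit on the claim. What remains is that recruiting staff can know the open cohort, and nothing in the plan prevents or records differential selection.

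**It would not be invisible.** A reader might also infer that any such selection would go wholly unseen. It would not: the CRF data on enrolled subjects would show imbalance in measured factors, and 9.4 lists minimum content, so a site may log more. That is a partial answer. No baseline comparison is planned, unmeasured differences stay hidden, and nothing obliges the site to log more.

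**Not all the evidence is exposed.** PSI against OAA/S can be examined within subjects, and section 6.3.5 allows Cohort 1 EEG to be reprocessed with candidate algorithms. This is fair; the point concerns the between-cohort comparisons of drug totals, wake-up times and somatic events.

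**It follows from the sequential design.** Largely so: concealed concurrent randomisation of Cohorts 2 and 3 would remove the differential part. The changes below are useful if the sequential design is kept.

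**Conclusion.** The point holds as a gap in safeguards, not as evidence of bias. The plan combines a predictable open cohort, two discretionary filters without stated criteria, no requirement to approach consecutive patients, and a log whose required content starts after the first filter. Differential selection between Cohorts 2 and 3 is therefore possible and would be only partly visible.

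Its size and direction cannot be derived from the documents. Under the assumptions of 25% complex cases and a 1 SD difference, the false-positive rate runs from about 6% to 24% as the share withheld in one cohort only goes from 25% to 100%. The 24% is the extreme of that scenario and should not be quoted alone. The case for acting is that the remedy is cheap and that unrecorded selection cannot be reliably reconstructed afterwards.

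**What to change.** - **Section 9.1:** approach consecutive patients on the elective schedule who meet 4.2 and 4.3, on recruiting days set in advance without regard to case mix, where there is time for a proper consent discussion. Limit the surgeon's input to those criteria and privacy needs, applied alike in every cohort.
- **Section 4.3:** require a recorded reason for each exclusion at the Principal Investigator's discretion. Without this, tying 9.1 to 4.3 would let undefined selection back in.
- **Section 9.4:** start a de-identified log at pre-screening, showing the cohort open at the time and the reason for any candidate not approached, within the scope of the IRB/HIPAA waiver.
- **Section 9.7:** report approached and enrolled fractions by cohort, and compare the baseline characteristics already collected, beside the Cohort 3 versus Cohort 2 comparison.

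The cost is protocol wording, slightly more log-keeping, less freedom in choosing cases, and possibly IRB confirmation of the log's scope, because the waiver described in section 4.5 is for identifying prospective subjects. The changes need to be in place before enrollment starts.

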### **9.2 Data Management and Confidentiality**

All documents associated with this protocol will be kept in the locked offices or on password protected computers. All data will be de-identified before any statistical analysis. Only de-identified data will be shared with Masimo for research purposes stated in this clinical investigation plan. Data collected by data capture software and data entered in case report form will be shared with Masimo via a secure, password protected server that only study staff and Masimo study team members will have access to. Blood specimens, if any are required per current clinical investigation plan, will be handled according to standard procedures for biological materials. Data will be retained for up to 2 years following completion of the final analysis.

### **9.3 Source Documents**

Source data is all information, original records of clinical findings, observations, or other activities in a clinical trial necessary for the reconstruction and evaluation of the trial. Source data are contained in source documents. Examples of these original documents and data records include: hospital records, clinical and office charts, laboratory notes, memoranda, recorded data from automated instruments, and copies or transcriptions certified after verification as being accurate and complete.

### **9.4 Screening and Enrollment Logs**

A subject screening and enrollment log will be provided to study site by sponsor, and maintained by study site. The screening and enrollment log will document, at a minimum, information such as the number of subjects approached for informed consent, the date of consent, subject eligibility, subject enrollment status, subject withdraw (if applicable) and reason(s) for withdrawal.

### **9.5 Case Report Forms**

9.5.1 The Sponsor shall provide a Case Report Form (CRF) template to the Site. The Site shall capture study data in the CRFs for each subject enrolled. The CRFs will be reviewed and signed by principal investigator. This also applies to those subjects who fail to complete the study. If a subject withdraws from the study, it is highly recommended that the reason(s) be noted on the CRF. Case report forms are to be completed on an ongoing basis. CRF entries and corrections will only be performed by study site staffs that are authorized by the investigator. Entries and corrections to the CRF will be made following Good Documentation Practices.

9.5.2 The CRF will include the following information, including but not limited to: inclusion / exclusion criteria, whether patient consent obtained before start of study, demographic information, event timing, anesthetic drugs used and dosage, patient skin condition after sensor removal, etc.

9.5.3 The CRF will be signed by the PI, and securely transferred to Masimo in pdf format.

9.5.4 CRF entries will be checked by Sponsor personnel after receipt and any errors or inconsistencies will be queried to the site on an ongoing basis. Query resolution will be assessed and confirmed by study monitor during site visit.

### **9.6 Data Transfer and Storage**

9.6.1 Device data will be captured through data capture software [REDACTED] and stored on a laptop. Device data along with a pdf copy of the CRF will be uploaded to sponsor via secure FTP portal after each study visit completion.

9.6.2 Only authorized sponsor personnel will have access to the uploaded data on the secure FTP portal, and will move it to a secure and backed-up drive at Masimo after receiving the upload from study site.

9.6.3 Device data and pdf copies of CRFs will be checked for completeness. If there are inconsistent or missing data points, a data query list will be generated and submitted to the site for corrections. [REDACTED]

### **9.7 Data Analysis**

Data analysis is to be done by Sponsor personnel upon completion of study. Data analysis may include descriptive statistics, regression testing and measures of accuracy (e.g., bias, precision and root mean square of the differences).

Different sets of comparisons could be made between the three Cohorts; data for Cohorts 2 and 3 may be compared against each other, and data for Cohort 2 and Cohort 3 may be compared individually against data for Cohort 1.

## **9.8 Record Retention**

Study data will be retained for the necessary period of time as required by the institution's regulations. Study Records shall be retained for a minimum of two years after study closure. The Institution's own retention policies and regulations may apply in addition to the minimal requirement.

## **10 MONITORING PLAN**

- 10.1 As the sponsor of this clinical investigation, Masimo Corporation is required by 21 CFR, Part 812, of the Food and Drug Administration regulations to monitor and oversee the progress of the investigation. The monitor(s) assigned by Masimo Corporation to this task will be employee(s) from the Clinical Research department who are trained on departmental SOPs and have adequate experience in conducting monitoring visits.
- 10.2 In accordance with good clinical practices guidelines, there will be at least three scheduled monitoring visits to ensure overall regulatory compliance of the study:
  - An initiation visit, prior to any subject enrollment to confirm site readiness, and to document training on the study protocol and procedures, and use of equipment.
  - At least one monitoring visit during enrollment, preferably when enrollment has reached 10% of subjects, and then at least once every year thereafter.
  - A final close out visit after the last patient had finished the study.
- 10.3 Study monitor(s) will initiate contact and setup on-site visits with the investigator. Study monitor(s) will be allowed, on request, access to all source documents needed to verify the entries in the CRFs and to all other GCP-related documents (IRB approvals, IRB correspondences, and ICFs) provided that subject confidentiality is maintained in agreement with HIPAA regulations.
- 10.4 It will be the monitor's responsibility to inspect the CRFs at regular intervals throughout the study, to verify the adherence to the CIP and the completeness, consistency and accuracy of the data being entered on them.
- 10.5 During each visit, the monitor will also verify presence of informed consent, adherence to the inclusion/exclusion criteria, and documentation of SAEs/SADEs and protocol deviations/violations, and check CRF against source documentation.
- 10.6 After each visit, the monitor will provide a monitoring report to the investigator within 4 weeks of visit completion. The monitoring report will detail findings and open action items observed during the visit. It is the responsibility of the Principal Investigator and Study Coordinator(s) to respond to the findings of the monitoring report, and complete any open action items as soon as possible but no later than 60 days of receiving the monitoring report. Any open action items not completed within the time allowed may be sufficient grounds for study site suspension or termination; it will be up to the sponsor to determine whether any incomplete action items are sufficient grounds for suspension or termination. See Section 13 for details on suspension and termination.
- 10.7 Depending on the quality of the data and/or changes to factors affecting patient safety, additional monitoring visits may be necessary at the sponsor's discretion.

## **11 PATIENT AND DATA SAFETY MONITORING AND REPORTING**

No monitoring by a data and safety monitoring board is planned. Standard of care anesthesia procedures will be in place for all cohorts, thus no additional risk is presented to subjects for participation in the study.

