#### **4.6 Withdrawal of Subjects**

Informed consent discussions will explicitly include emphasis that neither patient enrollment nor patient withdrawal from the study will result in any alterations to the standard clinical care. Subjects may elect to withdraw at any time up to the induction of general anesthesia.

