#### **6.5 Cohort 3**

- 6.5.1 Raw data from all the study sensors will be collected as described in Section 6.2 (Non-invasive readings).
- 6.5.2 The anesthesiologist and/or anesthesia providers will be able to monitor and use the investigational PSI Rev 2.X to supplement SOC procedures in managing anesthesia.
- 6.5.3 At the anesthesiologist's and/or anesthesia providers' discretion, he/she can discontinue his/her reliance on PSI and can revert to standard of care anesthesia procedures at any time to safeguard subject health, safety, and welfare.
- 6.5.4 All study data as described in this Clinical Investigation Plan will be provided to Masimo and analyzed.

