## **12 BENEFITS / RISK ANALYSIS**

- 12.1 There is no specific benefit to the individual subjects for participation in this research protocol.
- 12.2 The Masimo Radical-7 and Root devices, in addition to SedLine and Pulse Oximetry sensors are non-significant risk devices, and are currently FDA cleared to be used together in Adults.
- 12.3 The new (investigational) PSI algorithm is similar to the current (FDA approved) PSI algorithm but has new features to compute PSI.
- 12.4 Risks from all Masimo sensors are minimal since they are non-invasive and use biocompatible adhesives to adhere to the skin. The Masimo Radical-7 and Root monitor and accessories are non-significant risk (NSR) devices because they do not present a potential for serious risk to health, safety, or welfare of a subject and:
- The devices are non-invasive monitoring devices (not an implant); or
  - The devices are not used in supporting or sustaining human life; or
  - The devices are not used in diagnosing, curing, mitigating, or treating disease, or otherwise preventing impairment of human health; or
  - The devices do not present a potential for serious risk to the health, safety, or welfare of the subject.
- 12.5 Risks from Pulse Oximetry sensors: pulse oximetry sensors function by shining light through the fingers or toes of the patient in order to detect pulsation in the capillaries. These sensors are non-invasive due to their use of optical technology. As such they present minimal risk to the patient.
- 12.6 Risks from SedLine sensors: SedLine sensors are similarly to traditional EEG or EKG electrodes, they function by detecting electrical current naturally occurring in the human body. Just like traditional EEG and EKG electrodes, SedLine sensors are non-invasive and present minimal risk to the patient.
- 12.7 All patient-contact materials, including the adhesive used in Masimo sensors have undergone biocompatibility testing by original materials manufacturer.
- 12.8 Risks and Mitigations are detailed in the Investigator's Brochure (IB). Principal Investigator is responsible for reviewing and understanding the IB, and he/she is responsible for the training of all study staff in order to mitigate said risks.

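### Sections 4.6 and 11 say that enrolment changes no standard care and adds no risk, but Section 6.5 lets an investigational PSI inform anesthetic management in Cohort 3, and Section 12 does not assess that risk

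*Combined protocol and SAP*

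**What the plan says.** Section 11 opens with "No monitoring by a data and safety monitoring board is planned" and continues that standard anesthesia care applies in every cohort, "thus no additional risk is presented to subjects for participation in the study".

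Section 4.6 requires consent discussions to emphasise that "neither patient enrollment nor patient withdrawal from the study will result in any alterations to the standard clinical care". It also limits withdrawal to the period before induction.

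Section 6.5.2 says that in Cohort 3 the anesthesia providers "will be able to monitor and use the investigational PSI Rev 2.X to supplement SOC procedures in managing anesthesia". Section 6.5.3 lets them, at their discretion, stop relying on PSI and "revert to standard of care anesthesia procedures at any time to safeguard subject health, safety, and welfare".

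Aim Four in Section 2.1 evaluates the new PSI against the current one on somatic events, total anesthetic drug, wake-up times and agreement with the OAA/S.

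In Section 12, items 12.2 and 12.4 to 12.7 deal with the monitors, sensors and adhesives. For the algorithm, 12.3 says: "The new (investigational) PSI algorithm is similar to the current (FDA approved) PSI algorithm but has new features to compute PSI". Item 12.8 refers to the Investigator's Brochure for risks and mitigations. Section 8.2 lists two anticipated events: a mild allergic reaction to the sensor materials, and "Redness or skin irritation from sensor material and adhesives".

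**The concern.** The risk statement and the consent message describe a study in which care is the same with or without enrolment. The cohort procedures describe one in which an uncleared index is shown to the person managing the anesthetic, who may act on it. Both cannot hold for Cohort 3.

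What is at stake is mainly disclosure. Subjects decide before induction and cannot withdraw afterwards, and Section 12.1 offers them no specific benefit. If Section 4.6 is followed as written, Cohort 3 subjects are given an assurance that Section 6.5 contradicts. The IRB receives a risk section that assesses the cleared hardware but states no risk for the one item under test, the algorithm that Section 5 lists as the investigational device.

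**Working it through.** The check is a comparison of passages; apart from a head count, no arithmetic bears on it.

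1. **The plan's own benchmark for standard practice.** Aim One takes Cohort 1, where the provider sees neither PSI nor raw EEG, as the baseline for ordinary practice. Section 6.3.3 adds that all clinical interventions there follow the institution's standard care. Sections 6.4 and 6.5 have no equivalent line. Management without a displayed PSI is therefore the plan's reference point.

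2. **What Cohort 3 adds.** Section 6.5.2 adds the investigational index as an input to management. Section 6.5.3 provides a way back to standard care for the subject's protection. A way back presupposes that management may have moved away, and its stated purpose presupposes that this could matter for safety. Section 6.4 (Cohort 2) has no such clause, so the plan itself treats the investigational index differently from the cleared one.

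3. **What Aim Four presumes.** Agreement between PSI and OAA/S can be studied without anyone acting on the index. Drug totals, wake-up times and somatic events cannot: they reflect on the displayed PSI only if it can influence management.

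4. **Does the Section 11 inference follow?** Its premise, that standard care is in place in all cohorts, can be true, because PSI is used as a supplement. The conclusion does not follow, because in Cohort 3 something investigational is added to that care. The Section 4.6 statement is stronger, since it denies any change, and steps 1 to 3 contradict it directly.

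5. **What Section 12 covers.**
   - Monitors, sensors, adhesives: assessed in 12.2 and 12.4 to 12.7, with sensor risk called minimal. With the two skin reactions in 8.2, even this does not fit a claim of no added risk.
   - New algorithm: 12.3 describes it but states no risk.
   - Remainder: referred by 12.8 to a brochure that is not among the documents.

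6. **Head count.** Investigational index: up to 50 of 150 subjects (50/150 = 33%). Section 4.6 wording, counting Cohort 2 as well: up to 50 + 50 = 100 of 150 (67%). Events in 8.2: two, both from sensor contact; none concerns use of the index.

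7. **What does not depend on the Section 11 sentence.** Section 8.3 requires all adverse events to be recorded and reported, anticipated or not. Section 10 sets site monitoring, Section 13.4 sets termination for an unanticipated adverse device effect (UADE), and Section 14 has the principal investigator judge whether the study is safe to continue. None of them relies on Section 11.

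**The case against.** The best defence is that PSI only supplements standard care, no PSI-based dosing rule exists, and the provider can stop relying on the index at any moment. A precautionary clause is weak evidence of conceded risk. Cohort 2 uses a cleared index indicated for the operating room. Section 4.6 sits under withdrawal and may be meant only as an assurance that nobody's care suffers for joining or leaving. Section 4.5 requires the purpose and procedures to be explained, and an IRB reading the plan reads 6.5 as well.

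Most of this lowers the risk without making it nil, and nil is what Section 11 asserts. The narrow reading of 4.6 works for withdrawal but not for enrolment, which the sentence also names. The point about Cohort 2 stands: its subjects are affected by the wording, not by an investigational exposure.

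A reader might infer more than the documents support:

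- *That Cohort 3 cannot be compared with the others on dosing-related harm.* Sections 6.3.1, 6.4.1 and 6.5.1 apply Section 6.2 to every cohort, so EEG, SpO2, pulse rate, OAA/S, drug administration and anesthetic gas data are recorded throughout. Somatic events and wake-up times are comparison measures (6.2.8). They do not capture every harm, but they allow a partial comparison.
- *That safety surveillance as a whole rests on the Section 11 sentence.* Only the absence of a monitoring board stands next to it; the other safeguards are independent.
- *That the hazard of a misleading index was never assessed.* The Investigator's Brochure may do so. It would still leave Sections 4.6 and 11 uncorrected.
- *That the consent form misleads subjects.* The form is not available; only the message prescribed in 4.6 can be judged.

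**Conclusion.** The contradiction is in the plan's text and should be corrected. Sections 4.6 and 11 cannot stand beside 6.5.2, 6.5.3 and Aim Four, and Section 12 does not state a risk for the algorithm under test. The direct reach is Cohort 3, up to 50 of 150 subjects; the consent wording also needs correcting for up to 50 in Cohort 2.

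This is a fault of internal consistency and risk disclosure. It does not show that subjects are at material risk, that a safety board is needed, or that the cohort comparisons fail. The conclusion assumes that using PSI in managing anesthesia means it may influence management, which Aim Four also presumes. It is limited by the absence of the consent form and the brochure from the documents.

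**What to change.** Reconcile Sections 4.6, 11 and 12 with Section 6.5:

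- **Section 11:** delete the inference from standard care to no added risk. State that the displayed PSI may influence anesthetic management in Cohorts 2 and 3, and that in Cohort 3 it is investigational.
- **Section 12:** name the risk of management informed by a misleading PSI value.
- **Section 4.6:** align the consent emphasis with this, and check the consent form against it. Enrolment is sequential (6.1), so the wording must be right before Cohort 2 opens at the latest.

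Optionally, record index-related untoward events on the existing CRF in the same way in all three cohorts, with categories chosen by the investigator. Because the cohorts run one after another, any difference in rates would still be confounded with time.

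Do not simply add such events to 8.2. Section 8.1 defines a UADE as one the plan has not already identified, and UADE status triggers IRB reporting (8.3) and the termination rule (13.4). Listing dosing-related events could take serious ones out of that class. State that neither the optional recording nor the new Section 12 text removes any serious event from UADE reporting or from 13.4.

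The cost is an amendment, matching consent text, a less favourable risk statement to the IRB and, if the option is taken, a little CRF work. No dose or clinical rule is proposed, and care delivery does not change.
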